#### **Exclusion Criteria**

- I. Individuals less than 65 years of age at the time of bivalent booster vaccination.
- II. Individuals vaccinated with multiple brands on the same day or multiple vaccinations (same/different brand) within 3 days of each other
- III. For case population only:
  - a. Individuals that do not contribute follow-up time to both risk and control intervals. If individuals disenroll or reach the end of the study period during the risk window prior to accumulating any time for post-vaccination control intervals, they will be excluded.
  - b. Individuals who had a diagnosis of a stroke outcome during the stroke outcome-specific clean window.
  - c. Individuals who had a diagnosis of COVID-19 in the 30 days prior to the stroke outcome.

## 5.4 Risk and Control Intervals

The definitions for observation period, risk, and control windows are provided below.

### 5.4.1 Observation Period/Follow-Up

For each individual, the observation period will start from the day following bivalent booster vaccination date, i.e., day 1 after vaccination and until the earlier of 90 days post-vaccination, disenrollment, administration of a subsequent mRNA COVID-19 vaccine, death or study period end. Day 0 (date of vaccination) is not included in the observation period since we would not be able to attribute stroke outcomes on this day to the exposure.

#### 5.4.1.1 Secondary Analysis II: Influenza Vaccines

For each individual, the observation period will start from the day following high-dose or adjuvanted influenza vaccination date, i.e., day 1 after vaccination and until the earlier of 90 days post-vaccination, disenrollment, administration of a subsequent influenza vaccine, administration of any mRNA COVID-19 vaccine, death or study period end. Day 0 (date of vaccination) is not included in the observation period since we would not be able to attribute stroke outcomes on this day to the exposure.

### 5.4.2 Risk Window

The risk interval is defined as the time during which risk of a stroke outcome is hypothesized to be related to vaccination based on biological plausibility and clinical input (Table 2). The selected risk intervals for all stroke outcomes are days 1-21 and days 22-42. The 1-21 day risk interval was selected to align with the definition of stroke as used by the CDC in their RCA. The 22-42 day risk interval is selected to assess any difference in risk during this period, and to avoid any biases in risk estimates that may arise from a carryover effect from the vaccine exposure into the control interval. Implementing a split window addresses concerns that risk of the outcomes may not be constant throughout the risk period. Risk intervals will not be split further in an effort to preserve statistical power.

### 5.4.3 Control Window

The post-vaccination control interval is defined as all follow-up time during the observation period following a vaccination that is outside of the risk interval(s) until the earlier of 90 days post-vaccination, disenrollment, subsequent mRNA COVID-19 vaccination, death, or study period end. Individuals who only accrued data during the risk intervals will be excluded from the analysis.

## 5.5 Statistical Analysis

### 5.5.1 Descriptive Analysis

A descriptive analysis will be conducted to demonstrate the counts and percentages of each stroke outcomes by the covariates of interest. Counts and percentages will further be stratified by risk and control intervals. We will also summarize case fatality rate for each stroke outcome.

**Table 6. Descriptive Statistics**

Covariates	Data Sources
Age (Categorical)	Medicare Enrollment Database

Covariates	Data Sources
Sex CMS Medicare Race/Ethnicity HHS Region Urban/Rural Status Dual Eligibility Facility/Provider Type Reason for Entering Medicare	Medicare Enrollment Database Medicare Enrollment Database Medicare Enrollment Database Medicare Enrollment Database Medicare Enrollment Database Medicare Enrollment Database Medicare Enrollment Database
Outcome Setting  IP  OP-ED	Medicare Claims  Medicare Claims
Concomitant Influenza Vaccination – Same Day as Bivalent Booster Administration High-dose  Adjuvanted  Recombinant  Live-attenuated  Cell-cultured  Standard	Medicare Claims  Medicare Claims  Medicare Claims  Medicare Claims  Medicare Claims  Medicare Claims
Other Vaccinations – Administered During Risk/Control Intervals Pneumococcal	Medicare Claims
Prior COVID-19 diagnosis (relative to outcome date)  COVID-19 diagnosis in the 30 days prior  COVID-19 diagnosis in the 31 to 365 days prior	Medicare Claims  Medicare Claims
Presence of Medical Conditions Hospitalization (prior 12 months) Ischemic Heart Disease Hypercholesterolemia Hypothyroidism Chronic Kidney Disease Heart Failure Chronic Obstructive Pulmonary Disease Asthma Gout Obesity	Medicare Claims Medicare Claims Medicare Claims Medicare Claims Medicare Claims Medicare Claims Medicare Claims Medicare Claims Medicare Claims Medicare Claims

Covariates	Data Sources
Nicotine Dependency ITP Impaired Mobility Depression Charlson Comorbidities Index	Medicare Claims Medicare Claims Medicare Claims Medicare Claims
Nursing Home Measures (For Nursing Home Residents Follow-Up Analysis) Health Inspection Five-Star Rating Health Inspection - 1 Star Health Inspection - 2 Stars Health Inspection - 3 Stars Health Inspection - 4 Stars Health Inspection - 5 Stars	Nursing Home Compare Dataset Nursing Home Compare Dataset Nursing Home Compare Dataset Nursing Home Compare Dataset Nursing Home Compare Dataset
Quality Measure Five-Star Rating Quality Measure - 1 Star Quality Measure - 2 Stars Quality Measure - 3 Stars Quality Measure - 4 Stars Quality Measure - 5 Stars	Nursing Home Compare Dataset Nursing Home Compare Dataset Nursing Home Compare Dataset Nursing Home Compare Dataset Nursing Home Compare Dataset
For-Profit Status For-Profit  Non-Profit Government (Non-Veterans) Veterans Homes Nurse Aid Staffing Hours per Resident per Day Licensed Practical Nurse Staffing Hours per Resident per-day Registered Nurse Staffing Hours Per Resident per Day Average Number of Residents per Day	Nursing Home Compare Dataset  Nursing Home Compare Dataset Nursing Home Compare Dataset Nursing Home Compare Dataset Nursing Home Compare Dataset Nursing Home Compare Dataset Nursing Home Compare Dataset Nursing Home Compare Dataset
Population Construction Statistics (Case Counts by Inclusion/Exclusion Criteria)	Medicare Claims

## 5.5.2 Primary Analysis: SCCS with Post-vaccination Control Intervals

### 5.5.2.1 Incidence Rate Ratio (IRR) Estimation

For the primary SCCS analysis, the rates of the stroke outcomes following the bivalent booster doses dose will be evaluated by brand. This analysis will compare the stroke outcomes rates in the risk and control intervals using a conditional Poisson regression model. A Farrington-adjusted SCCS model will be implemented that adjusts for the reduced observation time that can occur from the occurrence of an outcome. We assume that only one incident event can occur in the observation period. Therefore, we only consider the first observed outcome.

$$\log(E(Y|X)) = \beta_1(\text{risk window}_1) + \beta_2(\text{risk window}_2) + \log(t) + \text{strata}(\text{pateint id})$$

$Y = \text{Stroke Outcome}$

$\text{risk interval} = \text{indicator for exposure}$

$t = \text{interval}$

$\text{patient id} = \text{term identifying the patient}$

Under this model, the null and alternative hypotheses for each risk window can be written as, respectively:

$$H_0: e^{\beta_1} = 1 \quad H_a: e^{\beta_1} \neq 1$$

$$H_0: e^{\beta_2} = 1 \quad H_a: e^{\beta_2} \neq 1$$

Where,  $e^{\beta_1}$  and  $e^{\beta_2}$  will be interpreted as the IRR for the stroke outcomes in the risk intervals compared to the control intervals. Thus, statistical significance of the coefficient on the risk interval variable at a pre-specified level will indicate a statistically significant association between COVID-19 vaccination and the stroke outcomes. Statistical significance will be determined using 95% CIs of IRRs and two-sided p-values ( $p \leq 0.05$ ).

#### 5.5.2.2 Attributable Risk (AR) Estimate

The study will also estimate the AR (per 100,000 doses and person-years). The number of excess stroke cases due to the vaccine will be directly derived from the conditional Poisson regression model, defined as the difference between the sum of the model fitted values (i.e., model predicted number of cases), and the sum of the expected cases if there were no vaccinations (i.e., all observed time is treated as control time). The AR is the excess number of stroke outcomes cases divided by the number of eligible beneficiaries (or eligible follow up dose-years). The standard error (SE) of the AR is estimated by bootstrap resampling 10,000 times. For each iteration, the study will sample the beneficiaries with stroke outcomes with replacement and repeat the AR calculation. The SE is calculated as the square root of the variance of the 10,000 AR values.

#### 5.5.3 Subgroup Analysis

For each stroke outcome, subgroup analyses will be conducted to assess the risk of stroke outcomes following bivalent booster vaccination by age group and concomitant influenza vaccination status. Prior to executing this analysis, a power analysis will be conducted to assess the feasibility of executing the subgroup analysis. For each stroke outcome, case counts by each subgroup will be determined, and used to estimate the minimum detectable IRR that will be observable in the subgroup analysis. These will be benchmarked against stroke outcomes risk estimates following either COVID-19 bivalent booster or third/monovalent booster doses available in the literature, to determine if there is sufficient power to detect previously referenced risk estimates.

#### 5.5.3.1 Age Subgroup Analysis

To evaluate difference in risk by age, a subgroup analysis will be conducted to assess bivalent booster risk by age group (65-74, 75-84, 85+) within the study population.

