On January 26, 2023 CDC presented these findings at a Vaccines and Related Biologic Products Advisory Committee meeting. At this meeting CDC noted that the risk of stroke in the population who had received a concomitant vaccination (receiving both a Pfizer-BioNTech COVID-19 Vaccine, Bivalent and a high-dose or adjuvanted influenza vaccines on the same day) was higher than the risk of stroke following receipt of the Pfizer-BioNTech COVID-19 Vaccine, Bivalent alone.

The NRS methods used by FDA and CDC have limitations and produce only a crude measure of association between an exposure and an outcome. A statistically significant result in these systems should be cautiously interpreted as it does not necessarily indicate an increased risk of adverse events of special interest (AESI) in the vaccinated population. Although the NRS systems adjusted for factors such as nursing home residency status, age, sex, and race, they did not adjust for any other potential confounding. In depth analyses which adjust for confounding are necessary to evaluate the signal.

The CBER Surveillance program has developed this protocol for use in conducting a more rigorous follow-up study of the results on the stroke outcomes identified in CDC VSD to determine whether there is an elevated risk using a more fully-controlled study design. This study will use a self-controlled case

series (SCCS) analysis to evaluate the preliminary stroke signal and the potential association between Pfizer-BioNTech COVID-19 Vaccine, Bivalent and stroke, including non-hemorrhagic stroke, hemorrhagic stroke, and transient ischemic attacks. The study will evaluate the Moderna COVID-19 Vaccine, Bivalent using the same methods. The study will also evaluate the risk of stroke outcomes following concomitant vaccination with a high-dose or adjuvanted influenza vaccine during the same study period. If a higher risk is identified post concomitant vaccination, this study will additionally evaluate the independent risk of stroke outcomes following high-dose or adjuvanted influenza vaccination.

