### 4.3 Outcomes

The stroke outcomes included in the study are hemorrhagic stroke (HS), non-hemorrhagic/ischemic stroke (NHS), transient ischemic attack (TIA), and a combined outcome which includes persons who have been diagnosed with non-hemorrhagic stroke and/or TIA (NHS/TIA). Risk following bivalent booster vaccination will be assessed separately for each of these stroke outcomes by vaccine brand. Stroke outcomes will be identified with International Classification of Diseases, Tenth Revision, Clinical Modification (ICD-10-CM) codes in either primary or secondary diagnosis positions.

The ICD-10 codes used to identify each stroke outcome, the care settings in which each outcome will be evaluated, as well as the clean and risk windows for each are described in Table 4. The first qualifying occurrence of the outcome in the observation period is defined as an incident stroke outcome only if no outcome of the same type was recorded during the preceding pre-defined clean window. The clean window is defined as a period prior to vaccination in which beneficiaries with an occurrence of an event during the pre-specified window are excluded because outcomes captured post-vaccination may be attributed to previous rather than incident risk. The risk window is defined as an interval post-vaccination during which occurrence of the stroke outcomes may be associated with the vaccine exposure and thus considered a qualifying outcome. Both clean and risk windows are selected based on literature review, consultation with subject matter experts, and to align with CDC definitions. Risk windows are further detailed in Section 5.4.2.

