#### 5.5.3.2 Concomitant Influenza Vaccination Analysis

To account for the possibility that the stroke outcome is occurring due to influenza vaccination or due to a combined effect between influenza and bivalent booster vaccination, a subgroup analysis will be conducted to assess stroke risk among beneficiaries with:

- I. Same day vaccination of a COVID-19 bivalent booster and a high dose or adjuvanted influenza vaccine
- II. A COVID-19 bivalent booster without any concomitant influenza vaccination (high-dose, adjuvanted, recombinant, or standard-dose). Concomitant vaccination defined as the receipt of a bivalent booster and a high-dose or adjuvanted influenza vaccine on the same day.

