### 5.5.6 Secondary Analysis II: Influenza Vaccines

If we observe a risk of any stroke outcome in the concomitant vaccinated subgroup, we will conduct a secondary SCCS analysis to evaluate the risk of that stroke outcome following high-dose or adjuvanted influenza vaccination (without concomitant bivalent booster vaccination). Similar to the primary analysis, this analysis will compare the stroke outcomes rates in the risk and control intervals using a conditional Poisson regression model. A Farrington-adjusted SCCS model will be implemented that adjusts for the reduced observation time that can occur from the occurrence of an outcome.

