## 5.6 Statistical Power and Sample Size Calculations

To ensure sufficient sample size, a power analysis will be conducted to evaluate the minimum detectable IRR for each of the stroke outcomes following COVID-19 bivalent booster vaccination, at 80% power and a two-sided alpha of 0.05. A minimum detectable IRR will be calculated at various data cutoff dates for the study, and the study cutoff data date will be determined based on an assessment of minimum risk detection at varied timeframes. A 90% threshold for data completeness is required at the specified data cutoff date to reduce differences in data accrual and the likelihood of observing events during risk relative to control intervals. Minimum detectable IRRs will be benchmarked against a comparable stroke outcomes risk estimate following either COVID-19 bivalent booster or third/monovalent booster doses present in the literature, to ensure sufficient sample size to detect the hypothesized IRR.

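### The age and concomitant-influenza subgroup analyses ask between-group questions, but the protocol specifies only within-subgroup IRRs and gives no estimate of the difference

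*Protocol*

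**What the plan says.** Section 5.5.3.1 gives the purpose of the age analysis: "To evaluate difference in risk by age, a subgroup analysis will be conducted to assess bivalent booster risk by age group", with groups 65-74, 75-84 and 85+. Section 5.5.3.2 allows that an influenza vaccine may by itself explain the strokes, or that they arise "due to a combined effect between influenza and bivalent booster vaccination, a subgroup analysis will be conducted to assess stroke risk among beneficiaries with". Its two groups are a same-day high-dose or adjuvanted influenza vaccine, and the booster without a concomitant influenza vaccine.

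Section 5.5.3 sets the planning basis: "case counts by each subgroup will be determined, and used to estimate the minimum detectable IRR" observable in the subgroup analysis. Section 5.5.2.1 gives the only model, which has two risk-window indicators, a time offset and patient strata. Its hypotheses set each IRR against 1, and "Statistical significance will be determined using 95% CIs of IRRs and two-sided p-values" at the 0.05 level. Section 5.6 plans "at 80% power and a two-sided alpha of 0.05". Section 4.3 multiplies the analyses: "Risk following bivalent booster vaccination will be assessed separately for each of these stroke outcomes by vaccine brand".

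The start of the influenza-only analysis is described in three places. Section 1 says "If a higher risk is identified post concomitant vaccination". Section 5.5.6 says "If we observe a risk of any stroke outcome in the concomitant vaccinated subgroup". Section 2.2 requires an increased risk after concomitant vaccination, limits the analysis to the outcomes concerned, and makes it subject to adequate power.

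**The concern.** A difference in risk by age, or between concomitant vaccination and the booster alone, is a contrast between two or more IRRs. The protocol defines the IRRs but not the contrast. A reader of the results would have a column of subgroup IRRs with intervals, and the natural but invalid step is to infer a difference where one is significant and another is not.

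The concomitant question matters most here. Section 1 reports that the earlier surveillance finding was itself comparative: stroke risk was higher with same-day influenza vaccination than with the Pfizer-BioNTech bivalent booster alone. A risk present equally in both groups would not point towards the influenza vaccine, yet nothing in the plan would separate that case from a risk confined to the concomitant group. The condition for the influenza-only analysis looks at the concomitant group alone, and its wording varies.

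**Working it through.** The protocol states no event count, achieved power or error rate for a subgroup comparison, so there is no figure to reproduce. The calculations below use its own design values.

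**Inputs.** Two-sided alpha 0.05 (Sections 5.5.2.1 and 5.6); power 80% (Section 5.6); three age groups and two concomitant-status groups (Section 5.5.3); four outcomes and two brands (Section 4.3); risk windows of days 1-21 and 22-42 (Section 5.4.2); control time of days 43-90, at most 48 days (Section 5.4.3).

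**1. Discordant significance when the true IRR is the same.** Let p be the power in each subgroup, with independent subgroups.
- Two groups: 2p(1 - p). At p = 0.80: 2 x 0.80 x 0.20 = 0.32.
- Three groups: 1 - p^3 - (1 - p)^3. At p = 0.80: 1 - 0.512 - 0.008 = 0.48.
- Actual subgroup power is unknown. At p = 0.90 the figures are 18% and 27%; at p = 0.50 they are 50% and 75%; with no effect (p = 0.05) they are 9.5% and 14%.

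A direct test of the ratio of IRRs would wrongly declare a difference 5% of the time per comparison.

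**2. Power of the contrast.** Take two subgroups of equal information, one with the IRR it can detect at 80% power and the other with IRR 1. The standardised effect within the first is 1.960 + 0.842 = 2.802. The difference has a standard error larger by the square root of 2, so the power is Phi(2.802/1.414 - 1.960) = Phi(0.021), about 51%.

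In events, with risk share r = 21/(21 + 48) = 0.304, an IRR of 1.5 within one subgroup needs (2.802)^2 / [(ln 1.5)^2 x r(1 - r)], about 226 events in the first risk window plus control. A ratio of IRRs of 1.5 between two equal subgroups needs four times as many: 4 x 226 = 904 in total.

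**3. Chance start of the influenza-only analysis.** The trigger sections do not say that observing a risk means statistical significance. If they mean a significantly raised IRR under the only decision rule given, there are 4 outcomes x 2 brands x 2 windows = 16 tests in the concomitant subgroup, each with a 2.5% chance of a false elevation. If independent, 1 - 0.975^16 = 0.333, or 33%.

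The tests are not independent: NHS/TIA contains NHS and TIA, and both windows share one control period. A simulation with these overlaps gives 28-29%. It assumes cases per brand for NHS, TIA and HS of 1000/600/300 or 400/250/150. These counts are not in the protocol, and the result hardly changes between them.

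**The case against.** The strongest reply is that the protocol never says it will read a difference from discordant significance. Section 5.5.3 defines subgroups and a feasibility check, and the model in Section 5.5.2.1 is introduced for the primary analysis. Objective II in Section 2.1 is worded as risk within groups, and a contrast could sit in a statistical analysis plan, which is not at hand. Part of this stands. A reader might infer that the concomitant question will be settled by comparing p-values, and the text does not say so. What remains is that Section 5.5.3.1 sets a difference as its aim, while the protocol fixes hypotheses and a subgroup power basis that contain none.

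A reader might also infer that one lone significant result launches the influenza analysis. That is not the protocol's wording either. Section 2.2 adds a power condition and restricts the analysis to the affected outcomes, and the check in Section 5.5.3 may reduce the number of tests. The three wordings can all be read as raised against the control window, so they are imprecise more than contradictory.

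A further stronger reading is that the influenza analysis should wait for a significant concomitant-to-alone ratio. The documents do not support that. With about 51% power in the case above, such a gate could suppress a safety follow-up, and a sensitive trigger is defensible in this setting. A false start adds one secondary analysis and changes no primary estimate.

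Finally, little information is lost as planned: the compared subgroups share no cases, so the ratio can be derived from the separate fits. That is correct, and it is why the remedy is cheap.

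**Conclusion.** The point holds as a mismatch between stated aim and specified method. Followed as written, the protocol produces no estimate of the difference by age or by concomitant vaccination. If subgroup significance were used in its place, equally affected subgroups would appear to differ 32% of the time (two groups) or 48% (three) at 80% power. Those figures assume equal power and independent subgroups, and they move with the power actually achieved.

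The trigger for the influenza-only analysis needs one definition. If it is any significantly raised IRR, it would fire by chance up to 33% of the time with no true effect, and less once overlap is allowed for. That bears on how a triggered analysis is read; it is no reason to withhold it. The main brand-specific IRRs are unaffected, so this is a change that should be made, not one on which the study's validity turns.

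**What to change.** In Section 5.5.3, for each outcome and brand, specify the ratio of IRRs between subgroups with its 95% CI for each risk window. It can come from risk-window by subgroup terms in the same Farrington-adjusted SCCS model: two terms for concomitant versus booster alone, and four for three age groups. Equivalently, it can come from the disjoint subgroup fits, with log ratio b1 - b2 and standard error the square root of (SE1^2 + SE2^2). State that any claim of a difference rests on this ratio, and label it exploratory.

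Reconcile Sections 1, 2.2 and 5.5.6 into one rule for starting the influenza-only analysis. The rule should say what counts as a risk, in which windows and brands, and how the power condition applies. Report the concomitant-to-alone ratio beside it to aid interpretation, without requiring it to be significant, and note the chance-trigger rate when interpreting a triggered analysis.

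The cost is a few model terms or a short calculation, with no new data. The drawback is wide intervals, which must not be read as evidence of no difference.
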